3.13.11 PedsQL

The PedsQL Measurement Model is a modular approach to measuring health-related quality of life (HRQOL) in healthy children and adolescents and those with acute and chronic health conditions (Varni et al, 2001). This will be conducted at FEVs, YEVs, and EDV or FV (as

applicable). Additionally, Last Assessment will be derived based on the last PedsQL assessment conducted post EV for each participant in EP0132.

The PedsQL Generic core module is a reliable and valid measure which has been used in a variety of health conditions and is responsive to change over time. It consists of 23 questions (or 21 items for the parent proxy report for ages 2 to ≤ 4).

Two versions are available: study participant self-report for ages 5 to ≤ 7 , 8 to ≤ 12 , 13 to ≤ 18 ; parent proxy report for ages 2 to ≤ 4 , 5 to ≤ 7 , 8 to ≤ 12 , 13 to ≤ 18 .

The PedsQL at the EV in EP0132 will be taken from the last visit in the N01269 analysis database. This will be applicable only for participants who discontinue early in N01269 and have an EDV assessment, or for participants having an unscheduled assessment after the last visit in N01269 and before or on the date of the EP0132 EV. The version of the PedsQL at the EV will be consistent with the version that was used at Baseline in N01269. All subsequent assessments of PedsQL in EP0132 will use the version consistent with the age of the participant at the time of assessment and will use the 1-week recall period version. Participants who turn 5 years old after the N01269 Baseline assessment will only have a parent proxy report at Baseline as there is no self-report for ages 2 to ≤ 4 .

PedsQL generic core scale scores will be calculated for each of the four PedsQL dimensions: Physical Functioning (8 items), Emotional Functioning (5 items), Social Functioning (5 items), and School Functioning (5 items [or 3 items for the parent proxy report for ages 2 to ≤ 4]). The PedsQL used in this study is retrospective to the prior week (acute version), and individual items are scored using a 5-point Likert scale (0 to 4 representing responses of: “never”, “almost never”, “sometimes”, “often”, or “almost always”), with the exception of the 5 to 7 year old participant-self-report, which has a scale of 0, 2, and 4 representing responses “not at all”, “sometimes”, and “a lot” respectively. The PedsQL generic item raw scores will be recorded in the eCRF.

These raw item scores of 0 to 4 will be transformed by the function: $100 - (\text{response} \times 25)$ in order to generate scores of 0, 25, 50, 75, and 100 where a higher value represents a better HRQoL. Each dimension score is then calculated as the mean of the transformed item scores from items of the considered dimension: items 1 to 8 for Physical Functioning, 9 to 13 for Emotional Functioning, 14 to 18 for Social Functioning and 19 to 23 for School Functioning (except for the parent proxy report for 2-4 year olds where items 19 to 21 constitute the School Functioning dimension). In the case of item-level missing data, these will be replaced by the average of non-missing item scores from the respective dimension, if at least 50% of the items from that dimension are non-missing.

Summary scores will also be generated:

- the Psychosocial Health Summary Score will be calculated as the mean of items (transformed scores after replacement of missing data) from the Emotional, Social, and School Functioning dimensions. However, in the case where the Emotional, Social, or the School Functioning scores would be missing, the Psychosocial Health summary score will be set to missing.
- the Physical Health Summary score (same as Physical Functioning dimension).
- the Total score will be calculated as the mean of all PedsQL items (transformed scores after replacement of missing data). However, in the case where one of the dimension

scores (Physical, Emotional, Social, or School Functioning) would be missing, the Total score will be set to missing.

The CFB in each dimension and summary score will be calculated separately for both PedsQL versions (participant self-report and parent proxy report) by subtracting the N01269 Baseline result from the EV/FEV/YEV/EDV/FV/Last Assessment result. This is re-written as a formula below:

$$CFB = \text{Score at timepoint} - \text{Score at Baseline}$$

Note that for participants aged 2 to 4 years old at N01269 Baseline, the CFB will not be calculated for the parent proxy report for assessments after the participant turns 5 years old as the 2 to 4 years old parent proxy report includes fewer items. For all other age groups, the CFB will be calculated across the different age versions of the report as the content of the reports are comparable. For example, the CFB for a participant aged 7 at Baseline will still be calculated when the participant becomes 8 years old and the 8 to \leq 12 years old self-report and parent proxy report are now completed.

A meaningful change in PedsQL scores is defined based on the Minimal Clinically Important Difference (MCID) values obtained in Varni et al, (2003) and presented in [Table 3-9](#). Note that the meaningful change categorization will not be assessed for the 2 to 4 years old parent proxy report.

For each PedsQL score:

- Improvement is defined as: $CFB \geq MCID$
- No change is defined as: $-MCID < CFB < MCID$
- Worsening is defined as: $CFB \leq -MCID$

Table 3-9: Thresholds to define meaningful change

Score	MCID (child self-report)	MCID (parent proxy report)
Total score	4.36	4.50
Physical Health	6.66	6.92
Psychosocial Health	5.30	5.49
Emotional Functioning	8.94	7.79
Social Functioning	8.36	8.98
School Functioning	9.12	9.67

MCID=Minimal Clinically Important Difference

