10.6.2 PedsQL

The absolute and CFB in total PedsQL score, Physical Health Summary Score, Psychosocial Health Summary Score, and Emotional, Social and School Functioning dimension score will be summarized using descriptive statistics. The Physical Functioning dimension will not be summarized as it is the same as the Physical Health Summary Score.

Summaries of the participant self-report will be reported over all age groups and separately for Young Children (ages 5 to 7), Children (ages 8 to 12) and Teens (ages 13-18), based on the participants age at N01269 Baseline. The summary over all age groups will exclude participants aged 2 to 4 years old since only a parent proxy report is available for this age group.

Similarly, summaries of the parent proxy report will be reported for all age groups and separately for Toddlers (ages 2 to 4), Young Children (ages 5 to 7), Children (ages 8 to 12) and Teens (ages 13-18). The summary over all age groups will exclude the 2 to 4 years age group as it includes fewer items. The summary for 2 to 4 years age group will include the absolute and CFB score only until the participant turns 5 years old (as CFB are not calculated for subsequent versions of the questionnaire for this age group).

The number and percentage of participants with meaningful changes in PedsQL score from N01269 Baseline will be presented at each visit. This will be presented separately for the participant self-report and the parent proxy report. Each dimension score (total scale score, physical health summary score, psychosocial health summary score, emotional functioning,

social functioning and school functioning) will be presented and the summary will be aggregated over all age groups. However, the summary will exclude the parent proxy report for participants 2-4 years' age group. The denominator for percentages will be the number of participants with a non-missing CFB score at the visit.

In addition, all available data for the PedsQL will be listed.

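### On the 5 to 7 year PedsQL self-report, fully answered at both time points, 'No change' in Emotional, Social and School Functioning means an identical score, and the pooled meaningful-change table hides this

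*SAP*

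**What the plan says.** SAP 3.13.11 scores PedsQL items from 0 to 4 on five levels, "with the exception of the 5 to 7 year old participant-self-report, which has a scale of 0, 2, and 4". Each response is transformed as 100 minus 25 times the response. "Each dimension score is then calculated as the mean of the transformed item scores from items of the considered dimension". Emotional, Social and School Functioning have five items each. A missing item is replaced by the mean of the answered items in its dimension, "if at least 50% of the items from that dimension are non-missing".

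Table 3-9 gives one column of child self-report MCIDs, used for every self-report age version. A change from Baseline (CFB) at or above the MCID is improvement, one at or below minus the MCID is worsening, and "No change is defined as: $-MCID < CFB < MCID". Only the 2 to 4 year parent proxy form is left out of this classification.

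SAP 10.6.2 reports means and changes by age group. The classes appear in one summary for self-report and one for proxy report: each score including "social functioning and school functioning) will be presented and the summary will be aggregated over all age groups".

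**The concern.** A three-way classification built on an MCID is meant to separate trivial from meaningful change. That works only if the score can take non-zero values below the MCID. On a three-level form with five items, the smallest movement may already exceed the threshold. The middle class then holds only children whose score is identical, and a single answer moved one level is reported as meaningful improvement or worsening.

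If so, the same label rests on different evidence depending on the form, and the pooled percentages depend partly on the age mix. There is no control arm to show the background rate of such classifications, and no planned summary table shows the classes for this form alone.

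**Working it through.** The plan states no computed figure on this point, so there is none to reproduce.

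**Inputs (SAP 3.13.11, Table 3-9).** Responses are 0, 2, 4 on the 5 to 7 year self-report and 0 to 4 on the other forms. Items number 8 (Physical), 5 (Emotional), 5 (Social) and 5 (School), so 15 for Psychosocial and 23 for Total. The child self-report MCIDs are in the table below.

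**Smallest step.** On the three-level form, responses 0, 2, 4 become 100, 50, 0, so one level is worth 50 points. On a five-level form it is worth 25. With k items answered at both time points, the step is 50/k or 25/k. Net steps needed = MCID/step, rounded up.

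| Score | MCID | Step, 3-level | Net steps | Step, 5-level | Net steps |
|---|---|---|---|---|---|
| Emotional | 8.94 | 10 | 1 | 5 | 2 |
| Social | 8.36 | 10 | 1 | 5 | 2 |
| School | 9.12 | 10 | 1 | 5 | 2 |
| Physical | 6.66 | 6.25 | 2 | 3.13 | 3 |
| Psychosocial | 5.30 | 3.33 | 2 | 1.67 | 4 |
| Total | 4.36 | 2.17 | 3 | 1.09 | 5 |

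For the first three scores, possible changes on the three-level form are 0, ±10, ±20 and so on. Only 0 lies inside the *No change* band.

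**Where this does not apply.**
- Unequal numbers of answered items give smaller non-zero changes: 2.5, 5 and 7.5 (5 against 4 items), 3.33 and 6.67 (5 against 3), 4.17 and 8.33 (4 against 3). All are below 8.36.
- A 5 to 7 Baseline form followed by the 8 to 12 form gives a smallest change of 5.
- Physical, Psychosocial and Total still need at least two net steps.
- The proxy forms that are classified have five levels; their step of 5 is below the proxy MCIDs of 7.79, 8.98 and 9.67.

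**Size under no true change.** Assume five independent items, each moving one level with probability m, up or down equally often. The chance of zero net movement is

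P0 = (1−m)^5 + 20(m/2)^2(1−m)^3 + 30(m/2)^4(1−m).

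On the three-level form, 1 − P0 are classed as changed:
- m = 0.10: 1 − (0.5905 + 0.0365 + 0.0002) = 37%
- m = 0.20: 1 − (0.3277 + 0.1024 + 0.0024) = 57%
- m = 0.30: 1 − (0.1681 + 0.1544 + 0.0106) = 67%

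On a five-level form, one net step is also *No change*, so subtract further

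P1 = 2[5(m/2)(1−m)^4 + 30(m/2)^3(1−m)^2 + 10(m/2)^5].

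**Comparing the forms.** Equal m is not equal noise, because one level is 50 points on one form and 25 on the other. Giving both forms the same latent noise (true item values uniform or skewed high, answers rounded to each form's grid), noise that changes 18-19% of five-level answers changes only 9-10% of three-level answers. False classification is then 10-11% on the five-level form and 35-37% on the three-level form. The formulas agree: 1 − P0 − P1 is 10.2% at m = 0.18 and 11.1% at 0.19; 1 − P0 is 34.5% at m = 0.09 and 37.3% at 0.10.

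**Effect on the pooled table.** The share of children on the three-level form is not given. Using mid-values of 10.5% and 36%, an assumed share of 10% gives 0.9 × 10.5 + 0.1 × 36 = 13%; 20% gives 16%; 30% gives 18%.

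**The case against.** The strongest reply is that the MCID is applied consistently in score units. A move from 0 to 2 on one item is 50 points on either form and shifts a five-item score by 10, so a child on a five-level form who makes the same move is also classed as changed. The three-level form simply cannot register anything smaller. This stands: the rule is not misapplied. It does not answer the point that the middle class no longer separates small from meaningful change, or that one table mixes forms for which the label differs in content. Whether these MCIDs suit the youngest form depends on the cited source, which is not available here.

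Other points also stand in part. The form follows the child's age at each assessment, so the affected group shrinks as children turn 8, and a constant share across visits is not supported. (Protocol 9.4.3 allows change from Baseline only on the same version. Under that rule, every comparison that uses this form would be of the affected kind.) Means and changes for ages 5 to 7 are planned separately and all PedsQL data are listed, although the age groups follow age at N01269 Baseline and so do not isolate the form used. Symmetric noise leaves improved minus worsened unbiased.

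A reader might infer three stronger things that the documents do not support:
- **Most children on this form would be falsely classed.** Under the assumptions above, that needs m above 0.157, and the documents give no value for m.
- **The contrast between forms is 57% against 12%.** That is the result at m = 0.20 on both forms, which gives the three-level form twice the noise in points.
- **The exclusion of the 2 to 4 year proxy form is a precedent.** The SAP's stated reason for handling that form differently is that it has fewer items, not that its scale is coarse.

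**Conclusion.** The point holds for Emotional, Social and School Functioning when the 5 to 7 year self-report is used at both N01269 Baseline and the visit with all five items answered each time. The minimum step of 10 then exceeds all three MCIDs, *No change* means an identical score, and the pooled table conceals it. This part is arithmetic and needs no assumption.

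The size does rest on assumptions (no true change, five independent items): 37% to 67% classed as changed for m from 0.10 to 0.30, or about 35-37% against 10-11% on a five-level form under equal latent noise. Neither the noise level nor the share of children affected is in the documents.

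Severity is minor. The classes supplement an exploratory change-from-Baseline endpoint, no hypothesis is tested, and no primary or secondary conclusion depends on them.

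**What to change.** In the SAP 10.6.2 meaningful-change table, show participants who completed the 5 to 7 year self-report at both N01269 Baseline and the visit in separate rows for all six scores. Define these rows by the form used, not by age at Baseline. Leave these participants out of the pooled percentages for Emotional, Social and School Functioning. Add a footnote that, with all items answered, the minimum step on this form (10) exceeds the MCID for these three scores. Add a matching sentence to SAP 3.13.11. Keep the planned absolute and change-from-Baseline summaries for ages 5 to 7.

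The cost is a few lines of SAP wording and a small programming change to one exploratory table. The drawback is that denominators will differ slightly between scores in that table.

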3.13.12 Dose from which study participant discontinued

The dose of study drug the study participant was taking the day they were discontinued from study will be derived as the most recent daily dose in mg reported in the Study Drug Collection Dispensation and Administration eCRF, prior to discontinuation for participants whose dose had been modified during the study. For participants whose dose has been maintained throughout the study, the prescribed starting dose of 100mg/day at the EV (or equivalently 2mg/kg/day for study

participants weighing less than 50kg) will be the dose from which they discontinued. The number of days the study participant received this dose will be calculated as follows:

Date of study discontinuation (or date of last dose if this is prior to date of study discontinuation) – the date of the first administration at the dose level from which they discontinued the study + 1.

The calculation assumes that any new dose is first taken the morning after it is dispensed. If a study participant discontinues from the study the day after a dose is modified, it will be assumed that they are discontinuing from the most recently modified (new) dose.

3.13.13 Dose at AE onset

The dose of study drug the study participant was taking at the onset of an AE will be derived as the most recent daily dose (in mg) reported in the Study Drug Collection Dispensation and Administration eCRF, prior to the onset date of the AE. AEs with onset date on the same day as a dose level change will be considered to have started prior to the dose change and will therefore be attributed to the preceding dose level. For AEs with an onset date on the same date as the EV, the dose at onset will be the prescribed starting dose of 100mg/day (or equivalently 2mg/kg/day for study participants weighing less than 50kg). For participants whose dose has been maintained throughout the study since the EV, the prescribed starting dose will be used as the dose at AE onset throughout the study.

The dose at AE onset will not be derived for AEs ongoing from N01269.

3.13.14 Day of last dose of study drug

The day of last dose of BRV is defined as the day of FV or EDV for participants who do not down-titrate, or the day of the DTV for participants who do down-titrate. For participants who are lost to follow up, the last dose of BRV will be the date of last dose as recorded on the Study Termination eCRF (imputed, if applicable, as described in [Section 4.1.4.5](#)).

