2.2 Study variables

2.2.1 Primary objective endpoints and estimands

Table 2-1: Primary objective

Objectives	Endpoints/estimands
To investigate the long-term safety and tolerability of BRV in pediatric study participants with CAE or JAE	
Treatment-emergent adverse events (TEAEs) 
Estimand: the estimand is defined by the following 4 attributes that will be used to define the treatment effect of interest for the primary safety analysis:
 
Population: population as defined in the protocol-specified inclusion/exclusion criteria reflecting the target patient population who receive at least 1 dose of BRV during the study.Study participant-level outcome: TEAE occurrence.Intercurrent event handling: The intercurrent event of concomitant medication use is handled by using a treatment policy strategy in which all TEAE data are included, regardless of receipt of any concomitant medication.The intercurrent event of treatment discontinuation is handled by using a while-on-treatment strategy where observation ends at 14 days after treatment is stopped. 
4. Population-level summary measure: incidence rates of TEAEs

Table 2-1: Primary objective

Objectives	Endpoints/estimands
To investigate the long-term safety and tolerability of BRV in pediatric study participants with CAE or JAE	
• TEAEs leading to discontinuation of study drug 
Estimand: the estimand is defined by the following 4 attributes that will be used to define the treatment effect of interest for the primary safety analysis:
 
1. Population: population as defined in the protocol-specified inclusion/exclusion criteria reflecting the target patient population who receive at least 1 dose of BRV during the study.2. Study participant-level outcome: TEAE leading to discontinuation occurrence.3. Intercurrent event handling: The intercurrent event of concomitant medication use is handled by using a treatment policy strategy in which all TEAE data are included, regardless of receipt of any concomitant medication.4. Population-level summary measure: incidence rates of TEAEs leading to discontinuation.
Primary objective	Secondary endpoints

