4.1.4.5 Handling of study medication with partial or missing date

No imputation should be performed for missing study medication start dates. This field on the eCRF should not be partial or missing.

The last dose of study medication for participants who down-titrate will be the last dose during the Down-Titration Period; for participants who do not down-titrate, the last dose of study medication will be the date of either the EDV or the FV (unless the participant reports stopping study medication earlier). For partial or missing date of last dose of study medication on the Study Termination eCRF, the following imputation rules will be applied for the purpose of calculating overall exposure:

- If only the month and year are specified, impute the last dose date as the earliest of the last day of the month or the date of last contact reported on the Study Termination eCRF. If the participant has died during the month use the date of death if this is earlier
- If only the year is specified, impute the last dose date as the earliest of the last day of the year or the date of last contact on the Study Termination eCRF. If the participant has died during the year use the date of death if this is earlier
- If the last dose date is completely unknown on the Study Termination eCRF and no information could be obtained from data cleaning exercises, then use the date of last contact unless the participant has died during the year, in which case use the date of death. A review of the data for study participants with completely unknown last dose dates should be performed to ensure that the imputation does not result in an unrealistic value for duration of exposure

Imputed date of last dose dates should only be used for calculation of the duration of exposure. The date as recorded on the eCRF should be presented in study participant data listings (no imputed dates should be included in study participant data listings).

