10.2 Adverse events

Adverse events will be summarized as reported on the EP0132 eCRF without integration of events from the N01269 analysis database. Any AEs that are ongoing at the time of entry into EP0132 will be entered on the EP0132 AE eCRF.

All AEs in this study will be classified as pre-treatment or treatment-emergent. In the following definitions, first dose of BRV refers to the first dose in EP0132. Pre-treatment AEs are defined as AEs which had an onset date prior to the first dose of BRV. Treatment-emergent adverse events are defined as AEs that had onset on or after the day of first dose of BRV. All summaries of TEAEs will be based on the SS. Summaries of TEAEs will be produced for the Overall Period, the Evaluation Period, and for each 3-month period in the Evaluation Period (as defined in [Table 3-3](#)), more details on the requirements of each period for each summary are provided in [Section 10.2.1](#).

For the reporting of UCB plain language summaries (PLS) additional summaries of TEAEs will be reported based on the SS. These will only be produced for the Overall Period.

For all summaries (with the exception of TEAEs leading to permanent discontinuation of study drug) the intercurrent event of treatment discontinuation is handled by using a while-on-treatment strategy where observation ends 14 days after treatment is stopped. Thus summaries will include all TEAEs with onset on or after the day of the first dose of BRV up to and including the date of last dose of BRV + 14 days, where missing or partial date of last dose is handled as described in [Section 4.1.4.5](#).

The standard AE eCRF has the outcome of “worsened” to be used when there is an increase in the intensity of an AE. The definition of “worsened” is when the AE is still present but at a heightened intensity. The eCRF instructions dictate to complete a new AE screen with the event term of the worsened event.

Note that the outcome of “worsened” is not allowed terminology within the CDISC standards. In the SDTM.AE, the data is mapped to the outcome “Not Recovered/Not Resolved”. The outcome of “Worsened” will be kept in SDTM.SUPPAE.

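### The SAP has two conflicting rules for the date of last dose, and it bars imputed last-dose dates from the 14-day adverse-event cutoff that relies on them

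*SAP*

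**What the plan says.** Five parts of the SAP bear on the date of last dose.

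- **3.13.14, the section titled as the definition.** "The day of last dose of BRV is defined as the day of FV or EDV for participants who do not down-titrate". Where there is down-titration, the date is instead fixed at the DTV. Only participants lost to follow-up get the date recorded on the Study Termination eCRF, imputed by 4.1.4.5 where needed.
- **3.13.15.** Total days on drug runs from first dose to the 3.13.14 date. Section 5.1.1 places this variable in the listing of participants who discontinued.
- **4.1.4.5.** For participants who do not down-titrate, the last dose is the EDV or FV date "unless the participant reports stopping study medication earlier". For those who do, it is the final dose taken during down-titration, which need not fall on the DTV date. After its imputation rules the section adds: "Imputed date of last dose dates should only be used for calculation of the duration of exposure".
- **10.1.** Exposure durations use the date of the final dose. For overall duration, missing or partial dates go to 4.1.4.5.
- **10.2.** Adverse-event summaries, except TEAEs leading to permanent discontinuation, include events "up to and including the date of last dose of BRV + 14 days, where missing or partial date of last dose is handled" by 4.1.4.5. This implements the estimand in SAP 2.2.1, a "while-on-treatment strategy where observation ends at 14 days after treatment is stopped".

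**The concern.** There are two separate problems.

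First, 3.13.14 and 4.1.4.5 give different dates for anyone who stops drug before the FV, EDV or DTV. A programmer who takes the section headed as the definition will use the visit date. One who takes 4.1.4.5 will use the reported date. The first choice counts drug-free days as exposure and moves the adverse-event cutoff later than the estimand intends.

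Second, 10.2 needs a handled date when the last-dose date is partial or missing, and it names 4.1.4.5 as the source. Section 4.1.4.5 says its imputed dates serve exposure only. Both instructions cannot be followed.

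At stake is whether the incidence of TEAEs, a primary endpoint, is counted over the window that its estimand defines, and whether the discontinuation listing shows correct time on drug.

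**Working it through.** The documents give no figure to reproduce here, so the check is date arithmetic plus a comparison of the sections.

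**Inputs.** The cutoff of 14 days is from SAP 2.2.1 and 10.2. The 90-day and 720-day thresholds are from SAP Table 10-1. Let T be the true days on drug and g the days from true last dose to the FV, EDV or DTV. The documents give no distribution for g or T. The values below are assumptions chosen to show a range.

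**Can g exceed zero?** Yes. Protocol Appendix 6 (10.6) tells sites to stop study medication at once when liver stopping criteria are met. It also says such participants should stay in the study until the work-up is finished. Drug can therefore stop before the closing visit.

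**Formulas if 3.13.14 is applied.**
- Days on drug = T + g, an overstatement of 100 × g / T percent.
- Cutoff, counted from the true stop = 14 + g days, against the intended 14.

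| g (assumed) | Cutoff after true stop | T = 80 | T = 350 | T = 700 |
|---|---|---|---|---|
| 0 | 14 days | 0% | 0% | 0% |
| 7 | 21 days | +8.8% | +2.0% | +1.0% |
| 14 | 28 days | +17.5% | +4.0% | +2.0% |
| 28 | 42 days | +35.0% | +8.0% | +4.0% |
| 60 | 74 days | +75.0% | +17.1% | +8.6% |

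If the same date were used for Table 10-1, 80 + 14 = 94 days would move a participant into the category of at least 3 months (90 days). Likewise 700 + 28 = 728 days would move one into at least 24 months (720 days).

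**Where the effect is certain and where it is conditional.**
- Certain when g > 0: 3.13.15 cites 3.13.14, so total days on drug in the 5.1.1 listing is too long by g.
- Conditional: 10.1 and 10.2 do not cite 3.13.14. They are wrong only if 3.13.14 is the rule programmed for them. They cite 4.1.4.5 for missing or partial dates, which does not settle which rule applies to a complete date.

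**Would another boundary catch the extra events?** Not before the visit. SAP Table 3-2 runs the Evaluation Period through the EDV or FV, so an event between the true stop and that visit stays inside the period. Only the 14-day rule can remove it.

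**The imputation conflict.** Take a participant whose Study Termination eCRF gives only month and year of last dose. Section 10.2 sends the cutoff to 4.1.4.5. That section produces a date, then confines it to duration of exposure. Read literally, the prescribed route yields no date for the cutoff. The default in 4.1.4.4 does not help: it settles whether an ambiguous event is treatment-emergent, not whether it falls within 14 days of last dose.

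**The case against.** The strongest reply is that the main analyses already point to the better rule. Sections 10.1 and 10.2 cite 4.1.4.5, which carries the exception for an earlier stop, and 3.13.14 already uses the recorded date for participants lost to follow-up. The planned course also keeps g at or near zero. A participant above the down-titration threshold is still on drug at the EDV or FV, then down-titrates and stops at the DTV. The purpose of 10.2 is clear, and the study is single-arm and descriptive.

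Much of this stands, and it limits the point. A reader might infer the following, which the documents do not support:

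- **That treatment-emergent status can be wrong.** It cannot on this ground: "Treatment-emergent adverse events are defined as AEs that had onset on or after the day of first dose of BRV". The last dose plays no part.
- **That both primary endpoints are affected.** TEAEs leading to discontinuation have no while-on-treatment cutoff in SAP 2.2.1 and are exempt in 10.2.
- **That the exposure tables are certainly wrong.** That depends on which rule is programmed.
- **That 3.13.12 contradicts 3.13.14.** Its wording, "or date of last dose if this is prior to date of study discontinuation", compares last dose with study discontinuation, which may be recorded after the closing visit. It shows only that the SAP expects the two dates to differ.
- **That gaps are long, or concentrated in early discontinuers.** No figure supports either.

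The reply does not remove the conflict. 3.13.14 still lacks the exception, 3.13.15 still inherits it, and the sentence limiting imputed dates still contradicts 10.2.

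**Conclusion.** The point holds as two internal inconsistencies. Following 3.13.14 gives false total days on drug in the discontinuation listing whenever drug stops g days before the visit. The effect extends to the exposure tables and to the adverse-event cutoff (14 + g days instead of 14) only if the same rule is programmed there. Separately, 10.2 and 4.1.4.5 cannot both be followed when the last-dose date is partial or missing.

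What can change is inclusion of events in the summaries cut at last dose + 14 days, primary TEAE incidence among them. The size cannot be stated, because the documents give neither the number of participants with g > 0 nor the number with incomplete last-dose dates. If every participant's last dose falls on the visit date and every date is complete, there is no error.

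**What to change.** Use one definition in both 3.13.14 and 4.1.4.5: the last-dose date recorded on the Study Termination eCRF. Impute partial dates by 4.1.4.5, and use the FV, EDV or DTV date only when the field is missing. Since 4.1.4.5 currently sends a wholly unknown date to last contact or death, state the order: the visit date if a visit was attended, otherwise the existing rule. With the recorded date, g = 0 and the cutoff falls 14 days after the true stop.

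Amend the restriction in 4.1.4.5 so that imputed dates also serve the 14-day cutoff in 10.2, while still keeping them out of listings. For consistency, have 10.1, 10.2 and 3.13.15 cite the same definition.

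The cost is a few sentences in the SAP and a check of which rule the derivation programs use. No new data are needed, because Table 3-2, 3.13.14 and 4.1.4.5 already rely on the Study Termination eCRF date.
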